6.1.18 End of Treatment Visit

Patients who have completed the study or have discontinued study treatment will be asked to return to the investigational site to have safety examinations and assessments within 7 days (± 3 days) after the last dose of the study drug.

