8.2 Adverse Event Reporting

8.2.1 Adverse Event Reporting Period

After informed consent, but prior to initiation of study drug, all AEs and SAEs regardless of attribution will be collected. After initiation of study drug, all SAEs and AEs regardless of attribution will be collected until 30 days after the end of treatment or start of a new antitumor therapy, whichever is earlier. After this 30-day period, and if the patient has not started any other antitumor treatment, then investigators should report only SAEs that are considered to be related to the study drug until study discontinuation.

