9.2.4 Safety Analysis

The summary of the exposure to study treatment, AEs, AESIs, AEs leading to drug modification or discontinuation including DLTs, changes in laboratory results, and changes in vital signs, etc, will be presented. The severity of all AEs will be graded according to NCI CTCAE v5.0, and the AE verbatim term will be coded by the Medical Dictionary for Regulatory Activities (MedDRA).

TEAEs are defined as AEs that started or worsened in severity on or after the first dose of study treatment and no later than 30 days after the end of treatment.

Only those AEs that were treatment-emergent will be included in summary tables. All AEs, treatment-emergent or otherwise, will be presented in patient data listings. The number and frequency of patients experiencing adverse events will be summarized according to system organ class (SOC) and preferred terms. If a patient reports a TEAE more than once within that SOC/preferred term, the AE with the highest severity will be used in the corresponding severity summaries.

The following safety summaries will be produced:

- Overview of AEs
- Summary of DLTs (dose escalation part)
- Summary of TEAEs
- Summary of serious TEAEs
- Summary of AESIs
- Summary of TEAEs leading to dose interruption, dose reduction, or termination of treatment

The above summaries will be repeated for TEAEs related to study treatment.

Drug exposure including number of cycles received, total duration of exposure, cumulative dose received (mg), dose intensity, and relative dose intensity will be summarized. The number and percentage of patients requiring dose interruption, dose delay, dose reduction, and treatment discontinuation because of AEs will be summarized. Reasons for dose modifications will also be summarized.

For laboratory tests that are graded by NCI CTCAE v5.0 or higher, results will be summarized by grade. Treatment-emergent changes will be summarized by maximum post-baseline grade. A shift table summarizing the shift from baseline to maximum post-baseline grade will be presented.

The changes in vital signs and ECOG PS scores from baseline will be summarized. Changes in 12-lead ECG (for example, changes in QTcF) will be summarized.

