15 APPENDICES

APPENDIX 1 PK/PD/BIOMARKER/ECG ASSESSMENTS FOR ESCALATION COHORTS

Study Day	Time Relative to Dosing	Study Drug Intake	Blood Sample for PK	Blood Sample for 2-HG	Bone Marrow Sample for 2-HG	Blood and Bone Marrow Samples for Gene Mutation Analysis	ECG
Screening				X	X	X ²	X
PK week Day 1	Predose ¹		X				X ³
	0 h	X					
	0.5 h (±2 min)		X				
	1 h (±5 min)		X				X ³
	2 h (±10 min)		X				X ³
	3 h (±10 min)		X				
	4 h (±15 min)		X				X ³
	6 h (±15 min)		X				
	8 h (±15 min)		X				
Day 2	24 h (±60 min)		X	X			
Day 3	48 h (±60 min)		X	X			
Day 4	72 h (±60 min)		X	X			
Day 5	96 h (±60 min)		X	X			
Day 6	120 h (±60 min)		X	X			
Day 7	144 h (±60 min)		X	X			
C1D1	Predose ¹		X	X			
	0h	X					
C1D8	Predose ¹		X	X			
	0 h	X					
C1D15	Predose ¹		X	X			
	0 h	X					
C1D22	Predose ¹		X	X			
	0 h	X					
C2D1	Predose ¹		X	X		X ²	X ³
	0 h	X					
	0.5 h (±2 min)		X				
	1 h (±5 min)		X				X ³
	2 h (±10 min)		X				X ³
	3 h (±10 min)		X				
	4 h (±15 min)		X				X ³
	6 h (±15 min)		X				
	8 h (±15 min)		X				
C2D2	Predose ¹		X				
	0 h	X					
C2D8	Predose ¹		X	X			

Study Day	Time Relative to Dosing	Study Drug Intake	Blood Sample for PK	Blood Sample for 2-HG	Bone Marrow Sample for 2-HG	Blood and Bone Marrow Samples for Gene Mutation Analysis	ECG
	0 h	X					
C2D15	Predose ¹		X	X			
	0 h	X					
C3D1	Predose ¹		X	X	X	X ²	X
	0 h	X					
C5D1	Predose ¹		X	X	X	X ²	X
	0 h	X					
C7D1 and every 3-cycles thereafter	Predose ¹		X	X	X	X ²	X
	0 h	X					
EOT (7 ±3 days after last dose)	Anytime			X	X	X ²	
Safety Follow-up visit (30 ±7 days after end of treatment)	Anytime						X

2-HG=2-hydroxyglutaric acid; C=cycle; D=day; ECG=electrocardiogram; EOT=end of treatment; IDH=isocitrate dehydrogenase; PD=pharmacodynamic(s); PK=pharmacokinetic(s); CCI [REDACTED]

¹ Blood sample collection should be performed within 30 minutes before the dosing on that day and approximately 24 (±60 minutes) hours after dosing on the previous day (ie, Day 1 of Cycles 1 or 2). Pre-dose bone marrow sample collection should be performed within 24 hours prior to dosing.

² Bone marrow and/or whole blood will be collected for analysis of gene mutation abundance, such as IDH1, IDH2 (R140 and R172), DNMT3A, NPM1, SRSF2, RUNX1, NRAS, KRAS, ASXL1, TP53, FLT3, PTPN11, CCI [REDACTED], etc.

³ Analysis for CCI [REDACTED] genes will be performed at baseline only.

³ To be performed in triplicate with intervals of approximately 5 minutes.

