4.1.4. Treatment Period

Unless otherwise specified, the treatment period is defined as the duration from the date of the first study drug administration to 30+7 days (7-day window only replies to parameters collected by visit) after the date of last administration of study drug or prior to the start of a subsequent anti-tumor therapy (whichever comes first). For safety data, only the assessments/events collected during the treatment period will be summarized.

The worst post baseline is defined as the worst assessments/events during the treatment period including both scheduled and non-scheduled visit. Only the on-treatment safety assessments will be included in the summary tables.

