4.4.2. Adverse Events (AEs)

All AEs will be coded from verbatim text to preferred term (PTs) and grouped by system organ class (SOC) using the Medical Dictionary for Regulatory Activities (MedDRA) version 27.1 or higher. AEs will be collected from the time of signature of informed consent throughout the treatment period. AEs will be graded by investigator according to National Cancer Institute (NCI) Common Terminology Criteria for Adverse Events (CTCAE) v5.0. Missing severity grade will not be imputed, and will be summarized as 'Missing Grade' category in the by-grade analysis.

An AE is considered a TEAE:

(i) If one of the criteria is met:

- 1) If the onset date is on or after the start of study treatment until 30 days after the last dose or prior to the start of a subsequent anti-tumor therapy (whichever comes first), or if the onset date is missing; or
- 2) If the AE has an onset date before the start of study treatment, but worsened in severity after the study drug administration (i.e. SAE start date is on or after the start of study

treatment until 30 days after the last dose or prior to the start of a subsequent anti-tumor therapy (whichever comes first);

(ii) Beyond 30 days after the last dose or after the start of a subsequent anti-tumor therapy (whichever comes first), treatment-related SAEs will also be considered as TEAEs.

Investigator assessed AEs causality to study drug will be classified as "Related" and "Not Related". An AE with a missing causality will be classified as "Related" to study drug.

Other AE variables include treatment-related AEs, AEs of special interest (AESI), COVID-19 related AEs, AEs leading to study drug modifications (i.e. dose interruption, dose reduction, or study drug withdrawal), AEs leading to death, and SAEs. The AESI information will be identified programmatically by SMQ/PT.

For AEs which are not on-going, duration of AE (days) is defined as AE end date – AE start date +1; for on-going AEs, the end date will be listed as 'Ongoing'.

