5.2.11.3. Death

Number of deaths and primary cause of death will be summarized descriptively. Similarly, the on-treatment deaths (i.e. deaths happening from first study drug administration to 30 days after the date of last administration of study drug or prior to the start of a subsequent anti-tumor therapy (whichever comes first)) and death during the follow-up period (i.e. deaths happening after 30 days after the date of last administration of study drug or prior to the start of a subsequent anti-tumor therapy (whichever comes first)) will also be tabulated.

All death information will be provided as patient list in which the on-treatment death will be flagged.

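### The SAP ends the TEAE window 30 days after last dose, the protocol 30 days after end of treatment; the nominal 7-day difference is not declared

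*SAP*

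**What the plan says.** **SAP.** Section 4.4.2 treats an AE as treatment-emergent "If the onset date is on or after the start of study treatment until 30 days after the last dose", or up to the start of subsequent anti-tumor therapy if that comes first. A second rule in the same section extends this in one direction: after that cut-off, "treatment-related SAEs will also be considered as TEAEs". Section 4.1.4 sets a general treatment period of 30+7 days after last dose, but the "7-day window only replies to parameters collected by visit", so the extra week does not reach AEs. Sections 4.4 and 5.2.11 repeat that restriction. Section 5.2.11.3 defines on-treatment deaths as "deaths happening from first study drug administration to 30 days after the date of last administration of study drug", again cut at subsequent therapy.

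**Protocol.** Section 9.2.4 defines TEAEs as starting or worsening from the first dose and "no later than 30 days after the end of treatment". Section 8.2.1 states that "all SAEs and AEs regardless of attribution will be collected until 30 days after the end of treatment" or the start of new antitumor therapy, whichever is earlier. Section 6.1.18 brings patients back for "safety examinations and assessments within 7 days" (±3) of the last dose; this is the EOT visit.

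**Declared changes.** SAP Section 7 lists eight departures from the protocol. None concerns the TEAE window.

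**The concern.** TEAEs and SAEs are part of the primary endpoint of Part 1 and Part 2 (protocol Table 3, SAP Table 1). If end of treatment means the EOT visit, the SAP closes the TEAE window about a week before the protocol closes both its TEAE definition and its AE collection. Sites would then report events that the protocol counts as treatment-emergent and the SAP's tables do not. Someone reading the study report against the protocol would not know, because the change is not declared.

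**Working it through.** Days are counted from the last dose.

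**Step 1: what end of treatment means in the protocol.** There is no formal definition, so the usage has to be set side by side.
- The synopsis (visit frequency) places treatment completion within 7 days (±3) after the last dose, so it is not the last-dose date itself.
- Section 6.1.19 times the Safety Follow-up visit at 30 days (±7) from the EOT visit. Appendix 1 times the same visit at 30 ±7 "days after end of treatment". The two terms are used for the same anchor.
- Where the protocol wants the last dose as anchor, it says so: the contraception period in inclusion criterion 9 runs 30 days from the last dose.
- As history only, the Amendment 4 log gives an AE collection limit of 37 days after last dose.

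**Step 2: the date arithmetic.** Protocol window end = day of EOT visit + 30. SAP window end = 30. Gap = the difference. At the nominal visit day, 7 + 30 = 37, which reproduces the figure in the Amendment 4 log.

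| EOT visit (days after last dose) | Protocol TEAE end | SAP TEAE end | Gap (days) |
|---|---|---|---|
| 0 | 30 | 30 | 0 |
| 4 | 34 | 30 | 4 |
| 7 (nominal) | 37 | 30 | 7 |
| 10 | 40 | 30 | 10 |

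The range depends on the text used. Appendices 1 and 2 put the EOT visit at 7 ±3 days after last dose, which gives a gap of 4 to 10 days. Section 6.1.18, the synopsis and the schedules of events put it within 7 days (±3), which allows about 0 to 10. If end of treatment meant the last-dose date, the gap would be 0.

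**Step 3: which events are affected.** For onset after Day 30 but inside the protocol window, with no new therapy started:

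| Event | Collected (protocol 8.2.1) | In SAP TEAE tables | In SAP listings |
|---|---|---|---|
| Non-serious AE, related or not | Yes | No | Yes |
| SAE judged unrelated | Yes | No | Yes |
| Treatment-related SAE | Yes | Yes, by the second rule | Yes |

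An unrelated fatal event with onset in that interval would be absent from the serious-TEAE and TEAE-leading-to-death tables, but present in the SAE and death listings.

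**Step 4: a consequence inside the SAP.** Appendices 1 and 2 schedule an ECG at the Safety Follow-up visit, nominally Day 37. The 30+7-day period admits that ECG to the summaries. A non-serious AE with onset on the same day, even one based on that ECG, is not a TEAE.

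**The case against.** The strongest reply is that the EOT-visit reading is an inference. Sections 9.2.4 and 8.2.1 say only end of treatment. Section 6.1.19 names the EOT visit when it means the visit, and Appendix 2 times the safety visit from termination of treatment, which could be the day drug stops. The SAP's extra 7 days may simply be the visit window of the Safety Follow-up, so it does not show that the SAP's authors accepted Day 37 as the AE limit. This stands as far as it goes: the term is ambiguous, and on a last-dose reading the gap vanishes. But the two timings of the same visit and the synopsis favour the EOT visit, and even the ambiguity needs resolving.

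Three stronger readings are tempting, and the documents do not support them.
- *The SAP always moves towards fewer events.* It does not. Its second rule keeps treatment-related SAEs with no stated time limit, which protocol 9.2.4 does not do, and it counts AEs with missing onset as TEAEs.
- *Events and deaths are lost.* They are not. SAP 5.2.11.2 lists all AEs, with separate listings of SAEs and of AEs leading to death. SAP 5.2.11.3 tabulates all deaths with cause before splitting them. The protocol has no on-treatment-death category, so a death on Days 31-37 is classed as a follow-up death and contradicts no protocol definition.
- *The loss can be sized from the protocol's 1.5-month median survival in refractory AML.* That would time deaths under an assumed survival curve, whereas TEAE status depends on AE onset. A fatal AE that began by Day 30 stays a TEAE whenever the patient dies.

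It is also fair to say that cutting the window at subsequent therapy is consistent with protocol 8.2.1, although 9.2.4 contains no such cut.

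**Conclusion.** The point holds as an undeclared change of anchor in a primary-endpoint definition. If end of treatment is the EOT visit, which the protocol's usage supports but does not state, the SAP's TEAE window is nominally 7 days shorter than the protocol's (about 0 to 10). The effect is confined to non-serious AEs and unrelated SAEs with onset in that interval, in patients who have not started new therapy, and to their place in the TEAE tables. The documents give no AE rate for that interval, so the number of events cannot be stated. The on-treatment-death split is a matter of consistency only.

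**What to change.** Define end of treatment once, in the SAP and in any further protocol amendment. Then take one of two routes.

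1. **Align.** In SAP 4.4.2, end the TEAE window 30 days after the EOT visit, or at the start of subsequent anti-tumor therapy if earlier, as in protocol 8.2.1. Apply the same limit to AEs that worsen after first dose, and keep the rule for later treatment-related SAEs. If no EOT visit took place, use last dose + 37 days. That fallback is a proposal (7 + 30) and is not in the current protocol text.
2. **Declare.** Keep 30 days after last dose, list it with a reason in SAP Section 7, and add a table of the AEs collected under protocol 8.2.1 that this cut-off excludes.

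Under either route, use the same cut-off in SAP 5.2.11.3 for consistency. Check concomitant medications too: protocol 9.2.3 runs to 30 days after end of treatment and SAP 5.2.7 to 30 days after last dose, also unlisted.

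The cost is a few lines of SAP text and one cut-off in the derivation program. The data are already collected. TEAE counts may rise slightly under the first route.

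### SAP 4.4.2(ii) counts late treatment-related SAEs as TEAEs with no end date, an undeclared departure from the protocol's closed window that mixes all-cause and related-only events in the same TEAE rows

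*SAP*

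**What the plan says.** **TEAE definition.** Protocol 9.2.4 defines TEAEs as AEs that begin or worsen "on or after the first dose of study treatment and no later than 30 days after the end of treatment". It makes no exception for related SAEs. It sends only TEAEs to the summary tables and all other AEs to listings. SAP 4.4.2(i) also has a closed window, ending 30 days after the last dose or at subsequent antitumor therapy. Item (ii) then reopens it: after that point, "treatment-related SAEs will also be considered as TEAEs". No end date is given. The same section sets missing causality to related.

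**Collection.** Under protocol 8.2.1, after dosing starts, "all SAEs and AEs regardless of attribution will be collected until 30 days after the end of treatment" or until new antitumor therapy, whichever is earlier. After that, provided no other antitumor treatment has begun, "investigators should report only SAEs that are considered to be related to the study drug until study discontinuation". Protocol 6.1.13 gives the same rule in substance. Protocol 8.6.8 makes a death more than 30 days after the end of treatment reportable as an SAE only if it is confirmed as related.

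**Summaries.** SAP 4.1.4 states: "For safety data, only the assessments/events collected during the treatment period will be summarized". SAP 4.4 repeats the limit. SAP 5.2.11 repeats it with a proviso for exceptions specified elsewhere. SAP 5.2.11.3 classes deaths after the window as follow-up deaths. SAP Section 7 lists eight changes from the protocol, and the wider TEAE definition is not among them.

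**The concern.** TEAEs, SAEs and deaths are among the primary safety endpoints in both parts, so item (ii) changes how a primary endpoint is defined without declaring it.

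The added events also come from a different collection rule. Inside the window an SAE enters the data whatever its cause. After the window an unrelated SAE is not requested and cannot be counted, while a related one can. A single percentage in the serious, Grade 3 or higher or fatal row then has no clear meaning: it is neither the incidence in a defined window nor the incidence over all follow-up. The tables are presented by dose level, and a cohort may have as few as 3 patients, so one such event is visible.

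**Working it through.** The plan has no figure for late SAEs to reproduce. Its only stated safety probabilities (protocol 9.1.2.2, n = 10) are correct: 1 − 0.90^10 = 65.1%, 1 − 0.95^10 = 40.1% and 1 − 0.99^10 = 9.6%. They do not bear on this point.

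**1. What item (ii) adds to the protocol definition.**
- A related SAE that starts more than 30 days after the end of treatment is not a TEAE under protocol 9.2.4 and is one under SAP 4.4.2(ii).
- A related SAE after new therapy is counted by item (ii), but protocol 8.2.1 no longer asks for it. Such events reach the database only if a site volunteers them.
- A late SAE with blank causality is set to related and so becomes a related serious TEAE.

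**2. Consistency inside the SAP.** A late related fatal SAE is a TEAE leading to death under 4.4.2 and 5.2.11.2. The same death is a follow-up death, not an on-treatment death, under 5.2.11.3. Read literally, 4.1.4 and 4.4 keep the event out of the summaries altogether.

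**3. Which rows mix collection rules** (SAP 5.2.11.2 counts patients, each once at the worst occurrence).
- Serious, Grade 3 or higher, fatal and SOC/PT TEAE rows: all-cause events in the window, related SAEs only afterwards. These rows are mixed.
- Any related TEAE: serious and non-serious related events in the window, serious only afterwards. This row is mixed.
- Related serious TEAE: the same event type is requested in both periods until new therapy. This row is not mixed, but its observation period is longer and varies by patient.
- Any TEAE: likely to move little, because a patient must have had no event in the window for a late one to matter.

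**4. Size.** Let x of n patients qualify from the window, and let k more qualify only through a late event. The row moves from x/n to (x + k)/n, a change of k/n. With k = 1:
- n = 3 (the minimum per dose level, protocol 4.1.1): 1/3 = 33.3 points.
- n = 6: 1/6 = 16.7 points.
- n = 12 (the size to which protocol 4.1.1 allows a cohort to be extended): 1/12 = 8.3 points.
- n = 40 to 50 (the planned total, protocol 9.1.2): 1/40 = 2.5 to 1/50 = 2.0 points.

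As an illustration with an assumed x = 8 and n = 40, 20.0% becomes 22.5%, 25.0% or 27.5% for k = 1, 2 or 3. The footnote to SAP Table 13 says only one patient was enrolled in Part 2, so the total may be below 40. If it were the 24 to 30 evaluable patients expected in escalation plus that one, the step would be 1/25 = 4.0 to 1/31 = 3.2 points. The value of k is not in the documents.

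**The case against.** The best defence is that counting late related SAEs is conservative: a serious harm attributed to the drug should not drop out of the incidence tables of a safety trial. The motive is sound, but the information is not lost without item (ii), because SAP 5.2.11.2 already lists all SAEs and all AEs leading to death.

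The conflict inside the SAP is also softer than the conflict with the protocol. SAP 4.1.4 opens its definition of the period, and 5.2.11 its summary rule, with a proviso for exceptions specified elsewhere, and 4.4.2 could be such an exception. That reading is possible, but 4.4.2 does not invoke it, the summary sentence in 4.1.4 and the text of 4.4 carry no proviso, and it does not reconcile the SAP with protocol 9.2.4. The lack of an end date has a practical limit too, since protocol 8.2.1 stops reporting at study discontinuation.

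Removing item (ii) does not equalise exposure either. The remaining window still depends on how long each patient is treated. That is true, but within it all events are collected under one rule.

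A reader might go further and infer that early, low-dose cohorts collect late events for up to 18 + 12 = 30 months against 12 for the last patients, a ratio of 2.5, and that the comparison of doses is distorted. The documents do not support this:
- Those figures are maximum total study time, built on an estimated recruitment period. Item (ii) starts only after treatment has ended, so time on treatment contributes nothing to it.
- Protocol 2.3.1 cites a median survival of about 1.5 months and 8% one-year survival in refractory AML, and requested reporting stops at new therapy. Few patients could approach the ceiling.
- No comparison of doses is tested, and escalation rests on DLTs in Cycle 1, which item (ii) does not touch.

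Nor do the documents show an inflated related share of events. The SAP tabulates patients and plans no such proportion.

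**Conclusion.** The point holds as a definitional and ascertainment problem. SAP 4.4.2(ii) widens a primary-endpoint definition beyond protocol 9.2.4, does not declare it in Section 7, and sits badly with SAP 4.1.4, 4.4 and 5.2.11.3. Several TEAE rows then combine all-cause events in the window with related-only events after it, and the related-serious row covers a longer period that varies by patient.

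The size cannot be stated. It is zero if no patient qualifies through a late event alone. Otherwise each such patient adds 1/n: 33 points in a cohort of 3, and 2 to 2.5 points at the planned total of 40 to 50. This rests on reading item (ii) as written and on late SAEs being collected as protocol 8.2.1 describes. No bias in the comparison between doses has been shown, and dose escalation decisions are unaffected.

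**What to change.** Remove item (ii) from the TEAE definition in SAP 4.4.2, so that the TEAE incidence tables use a closed window as in protocol 9.2.4. State the anchor once, since the protocol counts from the end of treatment and the SAP from the last dose. Report related SAEs after the window in a separate count and listing, with onset relative to the last dose and to any new therapy, and mark those whose causality was imputed as related.

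If the sponsor prefers to keep item (ii):
- declare it in Section 7 and cross-refer to 4.1.4 and 4.4;
- restrict it to events that the protocol collects, that is, before new antitumor therapy;
- show the related, serious and fatal rows with and without the late events.

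The cost is a few lines of SAP text and one extra output. The downside of removal is that late related SAEs sit outside the main incidence rows, so the safety text should point the reader to the separate count.
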